7.1. Severity

All AEs, both serious and non-serious, will be assessed for severity using the Common Terminology Criteria for Adverse Events (CTCAE) v5.0. The CTCAE scale includes unique clinical descriptions of AEs that are categorized by anatomy and/or pathophysiology. Reference the following website:

https://ctep.cancer.gov/protocolDevelopment/electronic_applications/docs/CTCAE_v5_Quick_Reference_8.5x11.pdf

The CTCAE scale displays Grades 1 through 5 with unique clinical descriptions of severity for each AE (including abnormal laboratory values) based on this general guideline provided in the CTCAE scale. For any AEs not covered by CTCAE the conventional definition of severity will be used.

- Grade 1 (Mild) AE: minor; no specific medical intervention; marginal clinical relevance
- Grade 2 (Moderate) AE: minimal intervention; local intervention; noninvasive intervention
- Grade 3 (Severe) AE: significant symptoms requiring hospitalization or invasive intervention
- Grade 4 (Life-threatening or disabling) AE: Complicated by acute, life-threatening complications; need for intensive care or emergent invasive procedure
- Grade 5 Fatal AE

7.2. Relationship

The investigator or qualified sub-investigator is responsible for assessing the relationship to study drug using clinical judgment and the following considerations:

- Related: The AE is definitely related to study medication administration.
- Probably Related: There is a high degree of certainty that the AE is related to study medication administration.
- Possibly Related: The AE could be related either to study medication administration or to concurrent disease/medication.
- Unlikely Related: There is a high degree of certainty that the AE is NOT related to study medication administration.
- Not Related: The AE is clearly due to other causes (e.g., concurrent medication, underlying disease, etc.)

The relationship to study-related procedures (e.g., invasive procedures such as venipuncture) should be assessed using the following considerations:

- Related: The AE is definitely related to study-related procedures.
- Probably Related: There is a high degree of certainty that the AE is related study-related procedures.
- Possibly Related: The AE could be related either to study-related procedures or to concurrent disease/medication.
- Unlikely Related: There is a high degree of certainty that the AE is NOT related to study-related procedures.
- Not Related: The AE is clearly due to other causes (e.g., concurrent medication, underlying disease, etc.). In making a causality assessment of an AE, consideration should be made as to whether or not the event is expected to occur due to the underlying disease based on the investigator's prior clinical experience in the management of aGVHD (see [Section 7.5.1](#)).

7.3. Clinical Laboratory Adverse Events

The investigator is responsible for reviewing the results of all laboratory tests as they become available and determining whether an abnormal value in an individual study subject represents a clinically significant change from the subject's baseline value(s). The investigator may repeat the laboratory test or request additional tests to verify the results of the original laboratory tests.

In general, abnormal laboratory findings without clinical significance (based on the investigator's judgment) are not to be recorded as AEs. However, laboratory value changes that require

treatment or adjustment in current therapy are considered AEs. Where applicable, clinical sequelae (not the laboratory abnormality) are to be recorded as the AE.

7.4. Serious Adverse Events

An SAE is defined by federal regulation as any AE occurring at any dose that results in any of the following outcomes:

- death,
- life-threatening AE (Note: A life-threatening AE is one that, in the view of the investigator, places the subject at immediate risk of death from the reaction as it occurred),
- hospitalization or prolongation of existing hospitalization,
- a persistent or significant disability/incapacity, or
- a congenital anomaly/birth defect.

Important medical events that may not result in death, be life threatening, or require hospitalization may be considered an SAE when, based upon appropriate medical judgment, they may jeopardize the subject and may require medical or surgical intervention to prevent one of the outcomes listed in this definition. Examples of such medical events include allergic bronchospasm requiring intensive treatment in an emergency room or at home, blood dyscrasias or convulsions that do not result in subject hospitalization, or the development of drug dependency or drug abuse.

An unexpected AE is any event for which the specificity or severity is not consistent with the AE profile in the current [EQ001 Investigator's Brochure](#).

All SAEs, regardless of cause(s) or relationship to study drug, must be reported within 24 hours to the study Sponsor and/or designee.

7.5. Reporting Adverse Events

7.5.1. Reporting Procedures for Non-Serious Adverse Events

The investigator is responsible for ensuring that all AEs observed by the investigator or designee or reported by the subject are reported using the AE eCRF.

The investigator will assign the following AE attributes:

- AE diagnosis or syndrome(s), if known (if not known, signs or symptoms)
- Dates of onset and resolution (if resolved)
- Severity
- Relatedness to study drug or study-related procedures
- Action taken
- Outcome

Follow-up of non-serious AEs will continue through the last day on the study and/or until a definitive outcome (e.g., resolved, resolved with sequelae, lost to follow-up) is achieved.

When a subject is withdrawn from the study because of a non-serious AE, the Sponsor and/or designee must be notified by e-mail or phone within 48 hours.

7.5.2. Reporting Procedures Serious Adverse Events

The investigator is responsible for ensuring that all SAEs observed by the investigator or reported by the subject are promptly assessed and reported to the Sponsor and/or designee. The investigator must assess whether the SAE is related to study drug or any study-related procedure.

The procedures for reporting SAEs are as follows:

- Record the SAE on the AE eCRF and complete the “Serious Adverse Event Report” form.
- Within 24 hours of the investigator’s knowledge of the event, e-mail, fax and/or enter via the electronic CRF the SAE Report form to the attention of the Sponsor and/or designee. Additional contact numbers and AE/SAE reporting instructions will be provided in the Study Manual.
- For fatal or life-threatening events, also e-mail and/or fax copies of hospital case reports, autopsy reports, and other documents, when requested and applicable. Transmission of such documents should occur with personal subject details de-identified, without losing the traceability of a document to the subject identifiers. Transmission of the initial report of the event should not be delayed in order to include these additional documents.
- The Sponsor or/or designee may request additional information from the investigator to ensure the timely completion of accurate safety reports.

The investigator must take all therapeutic measures necessary for resolution of the SAE. Any medications or therapies necessary for treatment of the SAE must be recorded in the event description section of the SAE form and the concomitant medication eCRF.

Follow-up of SAEs will continue through the last day on the study and/or until a definitive outcome (e.g., resolved, resolved with sequelae, lost to follow-up, fatal) is achieved.

While pregnancy is not considered an AE, all cases of fetal drug exposure via a maternal parent as study subject or pregnancy of a partner of a male study subject will be reported immediately to the Sponsor or its designee. Information related to the pregnancy must be documented on a “Pregnancy Confirmation and Outcome” form, provided by the Sponsor or its designee, and the pregnancy should be followed until a definitive outcome has been determined.

Some SAEs will qualify for reporting to the FDA as applicable via the MedWatch reporting system in accordance with FDA and other applicable regulations. The Sponsor or its designee will report SAEs as required to regulatory authorities, investigators in compliance with all reporting requirements according to local regulations and Good Clinical Practice (GCP).

The investigator will notify the appropriate IRB of SAEs occurring at the study site and other AE reports received from the Sponsor, in accordance with local procedures and statutes. The investigator or designee at each study site is responsible for submitting Investigational New

Drug (IND) safety reports (initial and follow-up) and other safety information (e.g., revised Investigator's Brochure) to the IRB and for retaining a copy in the study files.

A horizontal bar chart consisting of five solid black bars of different lengths. The bars are positioned side-by-side, with the longest bar on the right and the shortest bar on the left. The chart is set against a white background with no grid lines.

[REDACTED] [REDACTED]

[REDACTED]	[REDACTED]	[REDACTED]

[REDACTED]

[REDACTED]

A thick black horizontal bar with a thin black vertical bar to its left.

[REDACTED]

11 of 11

—

11 of 11

1

1 |

[REDACTED]

11 of 11

—

[figure not shown]
Page 1 of 1

Equilibrium, Inc.

Confidential

8. STUDY ACTIVITIES

Please refer to the Appendices, [Section 12](#), for additional details.

Horizontal bar chart showing the percentage of patients with various symptoms at baseline and after treatment. The y-axis lists symptoms: pain, fatigue, nausea, constipation, diarrhea, and others. The x-axis shows percentages from 0% to 100%. Bars are black with white outlines. The 'Others' category is the most prominent, especially at baseline.

Time Point	Pain	Fatigue	Nausea	Constipation	Diarrhea	Others
Baseline	10	10	10	10	10	80
Post-treatment	5	5	5	5	5	85

A horizontal bar chart showing the distribution of 1000 samples across 10 categories. The categories are represented by black bars of varying lengths. The x-axis is labeled "Category" and the y-axis is labeled "Sample ID".

Category	Sample ID	Length (approx.)
1	1	100
1	2	100
1	3	100
1	4	100
1	5	100
1	6	100
1	7	100
1	8	100
1	9	100
1	10	100
2	1	100
2	2	100
2	3	100
2	4	100
2	5	100
2	6	100
2	7	100
2	8	100
2	9	100
2	10	100
3	1	100
3	2	100
3	3	100
3	4	100
3	5	100
3	6	100
3	7	100
3	8	100
3	9	100
3	10	100
4	1	100
4	2	100
4	3	100
4	4	100
4	5	100
4	6	100
4	7	100
4	8	100
4	9	100
4	10	100
5	1	100
5	2	100
5	3	100
5	4	100
5	5	100
5	6	100
5	7	100
5	8	100
5	9	100
5	10	100
6	1	100
6	2	100
6	3	100
6	4	100
6	5	100
6	6	100
6	7	100
6	8	100
6	9	100
6	10	100
7	1	100
7	2	100
7	3	100
7	4	100
7	5	100
7	6	100
7	7	100
7	8	100
7	9	100
7	10	100
8	1	100
8	2	100
8	3	100
8	4	100
8	5	100
8	6	100
8	7	100
8	8	100
8	9	100
8	10	100
9	1	100
9	2	100
9	3	100
9	4	100
9	5	100
9	6	100
9	7	100
9	8	100
9	9	100
9	10	100
10	1	100
10	2	100
10	3	100
10	4	100
10	5	100
10	6	100
10	7	100
10	8	100
10	9	100
10	10	100

A horizontal bar chart illustrating the distribution of 1000 samples across 10 categories. The categories are represented by black bars of varying lengths, indicating the frequency or count of samples for each category. The distribution is highly right-skewed, with a few categories having a large number of samples and many categories having a small number of samples.

Category	Approximate Sample Count
Category 1	~950
Category 2	~800
Category 3	~700
Category 4	~600
Category 5	~500
Category 6	~400
Category 7	~300
Category 8	~200
Category 9	~100
Category 10	~50

9. PLANNED STATISTICAL METHODS

A detailed description of data analysis and statistical methods to be used will be outlined separately in a Statistical Analysis Plan (SAP).

9.3. Analysis Populations

9.3.1. Safety Population

Safety population consists of all subjects who receive any study medication. All data summaries except PK and PD data related summaries will use this population.

9.3.2. Pharmacokinetic Analysis Population

Subjects in the safety population who have at least one (1) measurable post-EQ001 exposure concentration will be included in the PK analysis population.

1

For more information, contact the Office of the Vice President for Research and Economic Development at [contact] or [contact].

1

9.3.4. Efficacy Population [REDACTED]

Subjects in the safety population who have received at least three (3) doses of study drug will be included in the efficacy population [REDACTED]

9.4. Subject Disposition

Subject disposition data will be summarized and will include number and percent of subjects enrolled, number and percent of subjects initiating and completing treatment, number and percent of subjects discontinuing treatment, and the reasons for discontinuation. Subject enrollment by study center and major protocol deviations will also be summarized.

9.5. Demographics and Baseline Characteristics

Demographics and other baseline characteristics will be summarized for the subjects in the safety population. Demographic data will include age, gender, race, and ethnicity. Baseline characteristics data will include (but not limited to) grade of aGVHD at diagnosis, organ involvement at diagnosis, underlying disease resulting in transplant, graft source, conditioning regimen, and prophylaxis regimen.

9.6. Statistical Analysis of Pharmacokinetic Variables

Serum concentrations and PK parameters ([REDACTED] [REDACTED] will be listed and summarized for EQ001 dose cohort using descriptive statistics by treatment for each cohort.

[REDACTED].

9.7. Safety Analysis

All safety data summaries will use the safety population.

For subjects in Part A, number and percent of subjects experiencing any DLTs will be presented by cohort. A listing of DLTs will also be provided.

AEs will be coded using the Medical Dictionary for Regulatory Activities (MedDRA) and will be graded by the investigator using the CTCAE v5.0 or the current version. Subject incidence of TEAEs, treatment-emergent serious AEs (TESAEs), TEAEs leading to treatment discontinuation and TEAEs with an outcome of death will be summarized by SOC and preferred term (PT). AEs will also be further summarized by worst severity grade and relationship to study drug. [REDACTED]

[REDACTED]

[REDACTED]

Clinical laboratory data will be summarized descriptively, these summaries will include observed values at collection timepoints and change from baseline. All laboratory parameters that can be graded using the CTCAE will be graded. [REDACTED]

[REDACTED]

[REDACTED]

[REDACTED]

[REDACTED]

[REDACTED]

[REDACTED]

[REDACTED]

[REDACTED]

9.9. Efficacy Analyses

[REDACTED]

[REDACTED]

[REDACTED]

[REDACTED]

[REDACTED]

[REDACTED]

[REDACTED]

All efficacy data summaries for Part A will use the safety population, whereas Part B will use the efficacy population for Part B. Clinical activity will be assessed by change from baseline in: aGVHD Organ Stages and Overall Clinical Grading and aGVHD-AI. Corticosteroid and immunosuppressive agent usage will be compared between groups. Overall mortality and nonrelapse-mortality at 12 months, overall response rate (proportion of subjects with a best response of PR or better during the 12-month assessment period compared to last pre-dose assessment) and Kaplan-Meier estimates of progression-free survival will also be calculated. In general, changes from baseline in numeric variables will be compared between the two groups using an analysis of covariance model with baseline value as a covariate. Proportions will be compared between the groups using the Fisher's Exact test. Time to event data will be compared using the log-rank test.

[REDACTED]

[REDACTED]

[REDACTED]

[REDACTED]

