2.2. Study Part B

2.2.1. Primary Objective

The primary objective of Part B of this study is to define the clinical activity of EQ001 in subjects with newly diagnosed aGVHD.

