3. INVESTIGATIONAL PLAN

3.1. Overall Study Design and Plan

This is a multi-center study to evaluate the safety, tolerability, PK, [REDACTED] and clinical activity of EQ001 in subjects with an initial clinical presentation of aGVHD. The study will enroll up to approximately 100 subjects in two (2) parts [REDACTED]

- Part A – Open-label, cohort based, dose escalation component:

Part A will enroll approximately 24 subjects in successive cohorts of 3 to 6 adult subjects each to determine the safety, tolerability, pharmacological, and biological activity of ascending IV doses of EQ001. Once an optimal dose is determined in Part A of the study, up to approximately 15 additional subjects will be enrolled at the selected dose in order to collect more data.

- Part B – Randomized, double-blind, placebo-controlled component:

[figure not shown]
Part B will enroll approximately 60 additional subjects, randomized in a 2:1 ratio to either active treatment with an optimally defined dose of EQ001 (40) or placebo (20), to determine the safety, tolerability, and clinical activity of EQ001.

Part A of the study will utilize a standard 3 + 3 dose escalation design until a dose is selected. Cohort enrollment will proceed in a sequential manner to evaluate the escalating dose levels of EQ001 (Section 5.3.1). Dose escalation will proceed as long as no predefined stopping criteria are met. The dose-limiting toxicity (DLT) assessment period will be the first 29 days of treatment (i.e., Study Days 1 to 29) and will guide dose escalation decisions. Subjects will be considered evaluable for DLT assessment if they have received at least two doses of study drug and completed through Study Day 29 or received at least one dose of study drug and had a DLT within the first 29 days on study. Enrollment of the next higher dose cohort will not commence until all safety data from all subjects from prior cohorts and all available safety data from the current cohort through Study Day 29 are reviewed by the Data and Safety Monitoring Committee (DSMC) and approval is granted for dose escalation. An optimal dose of EQ001 will be determined based on all available data, including safety, tolerability, [REDACTED]. Once a dose is selected, up to approximately 15 additional subjects will be enrolled at the selected dose in order to collect more data.

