Part B of the study will be randomized, double blinded, and placebo controlled, and will commence following the completion of Part A and approval by the DSMC. In Part B, approximately 60 subjects will be enrolled to better define the safety, tolerability, [REDACTED], and to explore the clinical activity of EQ001 in subjects with newly [REDACTED] [REDACTED] aGVHD.

[figure not shown]
After informed consent has been obtained, all subjects will be screened for potential participation, and those meeting eligibility criteria will be offered participation in the study. The study will enroll subjects with an initial clinical diagnosis of aGVHD requiring systemic immunosuppressive treatment. All subjects must receive their first dose of study drug within 72 hours (3 days) of the subject's initial systemically administered corticosteroid dose.

The systemically administered corticosteroid treatment will be prednisone, at approximately 1-2 mg/kg/day (or its equivalent) at the time of first dose of study drug administration; however, the investigator can adjust dosing as clinically indicated during the study according to the recommended treatment and tapering schedule [REDACTED]

Subjects in Parts A and B will have the same study assessments except as noted. All subjects will have two (2) months of dosing comprising five (5) doses of study drug, administered IV every fourteen (14) days, and ten (10) months of follow up for a total of twelve (12) months in the study. The follow-up period will consist of a 2-month Safety Follow-Up period (through Day 169) and then an 8-month Long-Term Follow-Up period (through Day 337). [REDACTED]

[REDACTED] overview of the study timeline for Part A and Part B, respectively. During the Long-Term Follow-Up period, the site will phone subjects on Study Days 253 and 337 to collect information on disease status (disease relapse or cGVHD), long-term survival, and safety (eg, recent hospitalization or SAEs).

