5.4.2. Prohibited Therapies

- [REDACTED]
- [REDACTED]
- [REDACTED]
- [REDACTED]
- [REDACTED]

If a determination is made to treat a subject with any these therapies or medications during the study, the Medical Monitor should be informed. Subjects will be asked to remain in the study and complete the remaining visits, but no additional study drug will be administered.

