7. ADVERSE EVENTS

An AE is any unfavorable and unintended sign (including an abnormal laboratory finding), symptom, or disease or any worsening of a pre-existing condition temporally associated with the use of a study drug, whether or not related to the study drug. AEs that occur after the first dose of EQ001 or during the study treatment and safety follow-up periods will be documented on the AE eCRF. The investigator will assess the AE severity and relationship of the AE to study drug. The investigator will treat the subject as medically required.

Laboratory values that are outside the laboratory reference range should be reported as AEs only if considered clinically significant by the investigator.

From the time of obtaining informed consent through the first administration of study drug, all SAEs and nonserious AEs related to protocol mandated procedures will be recorded on the SAE/AE eCRF. All other untoward medical occurrences observed during screening, including exacerbation or changes in medical history, will be captured on the medical history eCRF. Details on recording and reporting AEs are provided below.

AEs will be collected through Study Day 169 for subjects who complete study drug through Day 57. AEs will be collected through Study Day 85 for subjects who discontinue study drug early. Recent hospitalizations and SAEs, if applicable, will be recorded at the Day 253 and 337 visits.

The investigator's clinical judgment should be used to determine whether a subject is to be withdrawn due to an AE. In the event the subject requests to withdraw from study-related treatment, the subject should be asked to return for all remaining study visits through Study Day 169. In the event a subject is withdrawn from study, an early-termination visit should be completed.

All subjects experiencing AEs while on study drug, including clinically significant abnormal laboratory values, whether or not associated with use of the study drug, must be monitored until the condition returns to normal, returns to the subject's baseline, until the investigator determines the AE has reached a stable outcome and is no longer clinically significant, or the subject is considered lost to follow up.

If consent has not been withdrawn, all deaths should be reported through Study Day 337, even if study drug has been discontinued.

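### Part B efficacy is analysed only in subjects who reached a third dose, a post-randomisation filter that can bias the EQ001–placebo comparison in either direction and understates mortality

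*Protocol*

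**What the plan says.** The analysis set for Part B is fixed in Protocol Section 9.9: "All efficacy data summaries for Part A will use the safety population, whereas Part B will use the efficacy population for Part B". Section 9.3.4 defines it: "Subjects in the safety population who have received at least three (3) doses of study drug will be included in the efficacy population". The outcomes listed in 9.9 include 12-month overall and non-relapse mortality, overall response, progression-free survival, organ stage and grade, and steroid use.

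Section 9.3.1 says of the safety population: "All data summaries except PK and PD data related summaries will use this population". For Part B efficacy, that sentence and the one in 9.9 cannot both apply.

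On the design, Section 3.1 says "Part B will enroll approximately 60 additional subjects, randomized in a 2:1 ratio", and each subject has a course "comprising five (5) doses of study drug, administered IV every fourteen (14) days". Section 2.2.1 gives the purpose: "The primary objective of Part B of this study is to define the clinical activity of EQ001".

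For subjects who receive a prohibited therapy, Section 5.4.2 says: "Subjects will be asked to remain in the study and complete the remaining visits, but no additional study drug will be administered". Section 7 requires deaths to be reported to Day 337 even after dosing has stopped, unless consent is withdrawn.

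The SAP supplied describes Part A analyses only. Neither document shows an all-randomised population for Part B.

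**The concern.** Randomisation protects the comparison only while subjects are analysed in the groups to which they were assigned. Receiving a third dose happens about four weeks after randomisation, and treatment can affect it. Before that dose a subject may die, stop for uncontrolled drug-related toxicity, be judged by the investigator or sponsor unlikely to benefit (both in Section 3.2.2), or move to a prohibited therapy. Each of these is plausibly related to prognosis or to treatment.

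Four things follow:

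- Early toxicity or early failure on EQ001 can be filtered out, which flatters EQ001.
- Early failure on placebo can be filtered out, which flatters placebo and hides a real effect.
- In the mortality and progression-free survival analyses, no included subject can have died before the third dose. About four weeks of follow-up are therefore free of deaths by construction.
- Subjects randomised but never dosed are also left out, because the set is a subset of the safety population.

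The protocol uses the unfiltered set for uncontrolled Part A and the filtered set for randomised Part B, where the protection matters most.

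**Working it through.** **Inputs from the documents.** About 60 subjects at 2:1 gives 60 × 2/3 = 40 EQ001 and 60 × 1/3 = 20 placebo, matching Section 3.1. Five doses 14 days apart fall on Days 1, 15, 29, 43 and 57. Section 7 confirms the last of these ("AEs will be collected through Study Day 169 for subjects who complete study drug through Day 57"). Dose 3 is therefore due on Day 29. Section 9.9 names Fisher's exact test for proportions.

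**Assumptions, because the documents show no figures.** Two-sided 5% level; true response of 50%, 60% or 70%; 5% to 25% of an arm with fewer than three doses.

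**1. False difference with no drug effect.** Let p be the true response in all randomised subjects and e the share with fewer than three doses, all of them non-responders. Response in the filtered set is p / (1 − e). For p = 60% with 20% and 5% excluded: 0.60/0.80 = 75.0% and 0.60/0.95 = 63.2%, a difference of +11.8 points. Significance was found by exact enumeration of Fisher's test, with the number excluded in each arm taken as binomial.

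| True response, both arms | Excluded, EQ001 / placebo | Response in filtered set | Difference (points) | Significant in favour of EQ001 |
|---|---|---|---|---|
| 60% | none | 60.0% / 60.0% | 0 | 1.8% |
| 60% | 20% / 20% | 75.0% / 75.0% | 0 | 1.9% |
| 60% | 10% / 5% | 66.7% / 63.2% | +3.5 | 3.6% |
| 60% | 15% / 5% | 70.6% / 63.2% | +7.4 | 6.3% |
| 60% | 20% / 5% | 75.0% / 63.2% | +11.8 | 11.3% |
| 60% | 25% / 5% | 80.0% / 63.2% | +16.8 | 20.7% |
| 50% | 20% / 5% | 62.5% / 52.6% | +9.9 | 8.4% |
| 70% | 20% / 5% | 87.5% / 73.7% | +13.8 | 19.2% |

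Reversing the imbalance at 60% (5% of EQ001, 20% of placebo) gives −11.8 points and a 9.0% chance of a significant result favouring placebo.

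As a cross-check, 20,000 simulated trials of the 50%, 20% / 5% case gave +9.8 points. They gave p < 0.05 in either direction in 8.7% of trials, against 2.9% in all randomised subjects.

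**2. A real effect hidden.** Take true response of 75% on EQ001 and 50% on placebo, with 20% of EQ001 and 50% of placebo non-responders stopping early. EQ001: 0.75 / (0.75 + 0.25 × 0.80) = 0.75/0.95 = 78.9%. Placebo: 0.50 / (0.50 + 0.50 × 0.50) = 0.50/0.75 = 66.7%. The 25-point effect shrinks to about 12 points. Power falls from 45% to 13%.

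**3. Mortality.** If 8% die before dose 3 and 30% by study end, and nobody else is excluded, the filtered set shows (0.30 − 0.08)/0.92 = 23.9%.

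An early excess can vanish altogether. Suppose early deaths are 15% on EQ001 and 5% on placebo, followed by 20% mortality among survivors in both arms. All randomised subjects then show 0.15 + 0.85 × 0.20 = 32% and 0.05 + 0.95 × 0.20 = 24%. The filtered set shows 20% in both arms.

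**The case against.** **Bias is not inevitable.** It needs exclusion that is related to outcome and differs between arms in number or prognosis. With 20% against 5% excluded at random with respect to response, the difference is about zero and p < 0.05 occurs in about 4% of trials. Suppose instead that stopping is only partly related to response: 30% of non-responders and 10% of responders on EQ001, 7.5% and 2.5% on placebo. At 50% true response, the gap is then 4.9 points and p < 0.05 occurs in 5.0% of trials. A subject who stops early for toxicity may also be a responder, since Section 9.9 takes best response over 12 months. All of this stands, so neither the direction nor the size is known.

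**Later stops remain in the set.** This is correct. Only subjects with fewer than three doses are removed.

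**Text is blacked out around Sections 9.3.4 and 9.9, and no Part B SAP is supplied.** A supportive all-randomised analysis could exist out of sight. The finding is therefore limited to the visible text, but the visible sentence in 9.9 covers all Part B efficacy summaries.

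**Early deaths are still reported.** Section 9.7 tabulates fatal adverse events in the safety population. That does not repair the comparison of 12-month mortality in 9.9.

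**Section 9.3.1 is a general sentence and 9.9 a specific one.** A reader would probably follow 9.9. That leaves the filter in force and the conflict uncorrected.

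**Part B is exploratory, with no visible alpha.** The 5% level is indeed an assumption. Distortion of the estimate does not depend on it.

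**Follow-up after early stopping is unevenly described.** The synopsis ties the Day 169 assessment to completing dosing, and Section 7 ends adverse event collection at Day 85 for early stoppers. Yet Section 7 also asks subjects who withdraw from treatment to return through Day 169. This stands and adds to the work of the fix.

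**Conclusion.** The concern holds. On the visible text, a condition met or failed after randomisation decides who enters every efficacy analysis serving Part B's primary objective. Missing data do not force this rule: early stoppers are generally asked to stay on study, and deaths are collected to Day 337.

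At 60% true response with no drug effect, the false difference runs from 0 with equal exclusion to +3.5 points at 10% against 5% and +16.8 points at 25% against 5%. It changes sign when the imbalance is reversed. These figures assume that every excluded subject is a non-responder; weaker links to outcome give smaller distortions. Even with equal exclusion, absolute response is inflated under that assumption (60% becomes 75% when 20% are removed), and early deaths leave the mortality summary.

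The conflict between Sections 9.3.1 and 9.9 needs correcting whatever the size of the bias. Both should be settled before Part B is unblinded.

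**What to change.** Make all randomised subjects, analysed by assigned arm, the population for every Part B efficacy summary and test. All randomised and dosed subjects would be a fallback, but that set still omits anyone randomised and never treated.

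State in advance how subjects with fewer than three doses are scored: death as an event for mortality and progression-free survival, and stopping for other aGVHD therapy as non-response. The latter is a choice of estimand and must be written into the best-response definition in Section 9.9. There is a partial precedent for Part A in SAP Section 6.9.1, which scores an assessment made after new aGVHD treatment as progression.

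Keep the three-dose set as a labelled sensitivity analysis. Reword Sections 9.3.1, 9.3.4 and 9.9 and the synopsis to agree, and carry the same rule into the Part B SAP.

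The cost is mainly wording, with no added subjects. The passages on visits and data collection after early stopping must also be reconciled, so that response and progression can be scored for these subjects. Reported response rates may be somewhat lower than in the filtered set.
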